Appendix 5: Participant symptom questionnaire

1. Have you had a persistent cough for more than two weeks?
2. Have you lost weight in the last 3 months?
3. Have you experienced any drenching night sweats during the last 3 months?

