Participants who request to withdraw from the study or are lost to follow up will be referred back to the routine clinical service by the study team. Participants who develop a positive blood transcriptional biomarker at any point during longitudinal follow-up will then enter the LTBI treatment sub-study. Participants who develop a positive blood transcriptional biomarker or reach a study end point (Appendix 6) as a surrogate for progressive TB before 2 years, will be identified as progressors. Participants who complete 2 years follow up will be identified as non-progressors. Progressors and non-progressors will undergo routine clinical assessments to evaluate the need for any TB treatment when their participation in the study ends.

6. Recruitment and consent

Potential participants who meet the eligibility criteria will be identified by the routine tuberculosis clinical service and introduced to the study team. The study team will describe the study to these individuals, provide them with the participant information sheet, and answer their questions, in person, by telephone, by post or by email according to the participant's preferences. After at least 24 hours to consider this information, the study team will invite those who agree to participate to provide written informed consent.

For non-English speakers the study team will communicate with telephone translation services and provide translations of the participant information sheet and consent form. The original signed consent form will be filed in the study master file and a copy will be provided to the participant. All participants who are referred to the study team will be entered into a screening log with a record of their eligibility criteria, their decision to participate or reasons for declining to participate as appropriate.

7. Eligibility criteria

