Appendix 6: Study end points

Participation in the study will end with any one of the following events and participants will go on to have routine clinical assessments to evaluate the need for LTBI or active TB treatment.

1. 2 year follow up completed
2. Changes in chest radiography (airspace shadowing or lymphadenopathy) consistent with progressive/active TB with at least one yes answer in the symptom questionnaire.
3. Two yes answers in the symptom questionnaire.

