Appendix 11: Participant case record form

Participant details			
Name		UIN	
NHS no.		Hospital Site	
DOB	Age	Gender	Ethnicity
Address			
Screening questions			
Could you be pregnant (if applicable)?			
Do any of the following diagnostic categories apply to your past medical history? (please circle):			
HIV infection, diabetes, malignancy, autoimmune diseases, keloid scarring, any skin disease, allergy to local anaesthetic injection			
Do you take any of the following medication? (please circle):			
Anti-TNF, Corticosteroids, Azothioprine, Cyclosporin, FK506, Methotrexate, Tacrolimus			
Why were you referred to the TB clinic? (please circle):			
Recent TB contact, recent migration to the UK, occupational health screening, other			
Country of birth			
Date of entry to UK, if non-UK born			
If you have recently had contact with someone with TB, where was this? (please circle):			
Household, work, healthcare setting, transport, social contact, other			
If you have recently had contact with someone with TB, what was the date of the most recent contact?			
Have you been vaccinated with BCG? If so, what year was this?			
Have you been diagnosed with TB disease before? If so, what year was this?			
Have you recently had a tuberculin skin test done? If so, what date was this?			
Date of consent			
Pre-TST	Persistent cough for more than two weeks?		Continue 
Blood 	Weight loss in the last 3 months?		End study 
CXR 	Drenching night sweats during the last 3 months?		
Visit 1: Tuberculin skin test in each arm			
Lot number	Date	Administered by	Signed
Visit 2: Read TST induration, local anaesthetic, TST biopsy 1			
TST L induration	TST L photograph 	TST R induration	TST R photograph 
Lot Number (48hr)	Date	Administered by	Signed
TST biopsy 1 		Signed	
Visit 3: Local anaesthetic, TST biopsy 2			

Lot Number (Day 7)	Date	Administered by	Signed		
TST biopsy 2 		Signed			
Eligibility for cohort studies					
LTBI treatment study?	Yes 	No 	Longitudinal contact study?	Yes 	No 
Accepted and commenced LTBI treatment?				Yes 	No 

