Longitudinal study follow up assessments (mark with tick or cross)			Outcome (circle)
3 months		Persistent cough for more than two weeks?	Continue Treatment study End study
Blood	Weight loss in the last 3 months?		
CXR	Drenching night sweats during the last 3 months?		
6 months		Persistent cough for more than two weeks?	Continue Treatment study End study
Blood	Weight loss in the last 3 months?		
CXR	Drenching night sweats during the last 3 months?		
9 months		Persistent cough for more than two weeks?	Continue Treatment study End study
Blood	Weight in the last 3 months?		
CXR	Drenching night sweats during the last 3 months?		
12 months		Persistent cough for more than two weeks?	Continue Treatment study End study
Blood	Weight loss in the last 3 months?		
CXR	Drenching night sweats during the last 3 months?		
15 months		Persistent cough for more than two weeks?	Continue Treatment study End study
Blood	Weight loss in the last 3 months?		
CXR	Drenching night sweats during the last 3 months?		
18 months		Persistent cough for more than two weeks?	Continue Treatment study End study
Blood	Weight loss in the last 3 months?		
CXR	Drenching night sweats during the last 3 months?		
21 months		Persistent cough for more than two weeks?	Continue Treatment study End study
Blood	Weight loss in the last 3 months?		
CXR	Drenching night sweats during the last 3 months?		
24 months		Persistent cough for more than two weeks?	Continue Treatment study End study
Blood	Weight loss in the last 3 months?		
CXR	Drenching night sweats during the last 3 months?		
Notes			

LTBI treatment study follow up assessments (mark with tick or cross)				Outcome (circle)
4 weeks		Persistent cough for more than two weeks?		Continue End study
Blood		Weight loss in the last 3 months?		
		Drenching night sweats during the last 3 months?		
Missed doses in last 4 weeks?			Pill count?	
8 weeks		Persistent cough for more than two weeks?		Continue End study
Blood		Weight loss in the last 3 months?		
		Drenching night sweats during the last 3 months?		
Missed doses in last 4 weeks?			Pill count?	
12 weeks		Persistent cough for more than two weeks?		Continue End study
Blood		Weight in the last 3 months?		
		Drenching night sweats during the last 3 months?		
Missed doses in last 4 weeks?			Pill count?	
24 weeks		Persistent cough for more than two weeks?		Continue End study
Blood		Weight loss in the last 3 months?		
		Drenching night sweats during the last 3 months?		

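### The progressor label counts symptoms without regard to the answers recorded at entry, and the cough item has no look-back window

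*Protocol*

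**What the plan says.** Appendix 5 has three items. Two have a time limit: "Have you lost weight in the last 3 months" and "Have you experienced any drenching night sweats during the last 3 months". The third does not: "Have you had a persistent cough for more than two weeks".

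Appendix 6 turns the answers into end points. Item 3 is simply "Two yes answers in the symptom questionnaire". Item 2 is a radiographic change "consistent with progressive/active TB with at least one yes answer in the symptom questionnaire". Neither requires the symptom to have appeared since entry.

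Section 5 then uses these end points to define cases. Participants who become biomarker positive "or reach a study end point (Appendix 6) as a surrogate for progressive TB before 2 years, will be identified as progressors". Those who complete 2 years are non-progressors.

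The case record form (Appendix 11) asks the same three items before the TST and at each visit from 3 to 24 months, with cough printed as "Persistent cough for more than two weeks". The pre-TST row has boxes to continue or to end the study, but no rule links either box to the answers. Section 7.2 excludes people with clinical or X-ray signs of active TB.

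**The concern.** The end points stand in for progression after entry, so a symptom that was already there carries no information about progression. As the rule stands, a cough present at entry supplies one of the two answers that Appendix 6 item 3 needs, at every visit. It also meets the whole symptom part of item 2, although a radiographic change is still required there.

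The people affected are those with long-standing cough from any cause, so the error is selective. The progressor group is expected to number only 20. Section 9.1 plans an outlier analysis that looks for expression patterns shared by subsets of progressors and claims power above 0.8 once 5 or more share a trait. A handful of wrongly labelled participants with a common non-TB characteristic is the kind of subset that such an analysis could pick up, if that characteristic affects the TST response. The documents do not say whether it does.

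**Working it through.** **The plan's own figure.** Section 9.1 takes 400 contacts and 5% progression: 400 × 0.05 = 20 progressors and 400 × 0.95 = 380 non-progressors. This reproduces exactly.

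**Windows against visits.** Longitudinal visits are 3 months apart for 2 years: 24 / 3 = 8 visits. The 3-month recall for weight loss and sweats equals the visit spacing, so a resolved episode of either counts about once. Cough is the only item without a limit.

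**Illustration for Appendix 6 item 3.** From the documents: 380 true non-progressors, 8 visits, two of three items positive. Assumed, because the documents give no symptom frequencies:
- c = share with a lasting cough at entry, 2–10%
- w = chance of a non-TB yes per visit on each of weight loss and sweats, 1–5%
- a = chance of a new cough per visit in the others, 1%
- items and visits independent, and both answers given at the same visit (Appendix 6 does not say so).

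Per-visit chance of two yes answers:
- cough carried from entry: 1 − (1 − w)²
- no cough at entry: a[1 − (1 − w)²] + (1 − a)w²
- cough at entry, not counted: w²

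The chance over 8 visits is 1 − (1 − p)^8 for each per-visit chance p. Expected false progressors among 380:

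| c | w | As written | Entry cough not counted | Excess |
|---|---|---|---|---|
| 2% | 1% | 2.0 | 0.9 | 1.1 |
| 5% | 2% | 7.5 | 2.3 | 5.2 |
| 10% | 5% | 30.6 | 10.1 | 20.5 |

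The excess reduces to 380 × c × [(1 − w²)^8 − (1 − w)^16], which does not involve a:
- 7.6 × (0.9992 − 0.8515) = 1.1
- 19 × (0.9968 − 0.7238) = 5.2
- 38 × (0.9802 − 0.4401) = 20.5

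**Effect on the case group.** If all 20 true progressors are found, the true share of the group in the middle row is 20 / 27.5 = 0.73 as written, against 20 / 22.3 = 0.90 with the entry cough not counted. In the bottom row it is 20 / 50.6 = 0.40 against 20 / 30.1 = 0.66.

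**Sensitivity.** Section 5 requires the end point before 2 years. If the 24-month visit is therefore left out, 7 visits remain and the ends of the range become 7.6 × (0.9993 − 0.8687) = 1.0 and 38 × (0.9826 − 0.4877) = 18.8. The conclusion is the same.

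**The case against.** The best defence is that entry is guarded. Signs of active TB exclude, and the pre-TST form allows the study to be ended on the same three answers. This removes some symptomatic people, but no rule says that a single yes excludes or is later discounted. A chronic cough with another explanation is not a listed exclusion. The guard is partial.

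The sizes also rest on assumed frequencies. Independence across visits raises the cumulative figure if yes answers cluster in the same people. That stands, and the low end, about one extra false progressor, is small.

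Three stronger readings are tempting but not supported.
- A reader might infer that a cough that resolved before enrolment must still be answered yes at month 12. That needs the cough item to mean ever; the case record form wording reads more like a current symptom. The chronic-cough problem does not depend on this.
- A reader might infer that old weight loss or sweats are rescored as new at the longitudinal visits. Their windows match the visit interval, so they are not.
- The sub-study form ("LTBI treatment study follow up assessments (mark with tick or cross") repeats the 3-month items at weeks 4, 8 and 12, so about 13 − 4 = 9 weeks of recall precede the previous visit, and a reader might count this as false progression. Sub-study participants were either biomarker positive at recruitment and not routed to longitudinal follow-up, or converted and are already progressors. Their answers there cannot add a progressor; at most they end sub-study participation.

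**Conclusion.** The point holds for the progressor label. Section 5 and Appendices 5 and 6, followed exactly, let a cough present at entry supply half of Appendix 6 item 3, or the symptom part of item 2, in the primary case definition. On the assumed inputs the excess through item 3 is about 1 to 20 false progressors against 20 expected true ones. It should be quoted as a range and as a net figure: counting every event among people with an entry cough would include some that two new symptoms would have produced anyway. No estimate is offered for item 2. The false progressors that remain after the correction (0.9 to 10.1 in the table) come from using symptoms as a surrogate at all, which is a separate matter.

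**What to change.** Change the analysis label only.

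1. In Section 5, state that a symptom counts toward the progressor label only if it is answered yes at follow-up and was answered no pre-TST.
2. For the label, give cough the same 3-month window as the other two items, for example by a follow-on line on the case record form, so that the existing question still serves its other purpose.
3. Leave the Appendix 6 stopping rules and the clinical assessment that follows them unchanged.
4. Participants who stop only because of a symptom already present at entry would be neither progressors nor 2-year completers. Classify them through the surveillance-record linkage that Section 9.2 already plans for withdrawals and losses to follow-up, and name them there.

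The cost is a few lines of text and one form entry; the pre-TST answers are already collected. The downside is that worsening of a symptom present at entry would not by itself count toward the label. Such cases would depend on the biomarker, on a radiographic change together with a new symptom, or on a linked TB record. Participants treated for LTBI after stopping may also have a lower chance of appearing in the linked records, which the report should state.

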The longitudinal study will recruit individuals with LTBI from the existing UK contact screening program^{11,27}. The additional individuals for the cross-sectional study will be recruited from the Public Health New migrant screening program referrals to LTBI clinics. Clinical staff at each participating site (Appendix 1) will introduce potentially eligible individuals (Section 7) to the study team, who will seek to obtain informed written consent (see Section 6). The study schedule for participants who give consent is summarised in Appendix 2. They will undergo a chest radiograph (provided by the routine NHS Trust clinical service) and screening blood tests (Appendix 3) and, followed by one tuberculin skin test in each arm. One TST site will be biopsied at 48 hours and the second TST site will be biopsied at seven days (Appendix 4). All blood tests, chest radiography, TSTs and biopsies will be performed within the TB clinic the participant was recruited from.

Participants who have a positive blood transcriptional biomarker will then enter the LTBI treatment sub-study. In the absence of clinical evidence of active TB, they will be offered LTBI therapy as part of their usual NHS care, and asked to attend appointments after 4, 8, 12 and 24 weeks for clinical review and repeat blood sampling (the 4, 8 and 12 week time points are aligned with those required in routine clinical care for monitoring). Adherence to LTBI therapy will be measured by self-report questionnaire, pill counts, urine testing and/or medication boxes, depending on local site availability and practice.

Participants with a negative blood transcriptional biomarker and who meet the eligibility criteria for the longitudinal study will be asked to attend follow up clinic appointments with the study team at three monthly intervals for two years. These additional appointments will take place at the TB clinic the participant was recruited from. At each appointment they will complete a questionnaire (Appendix 5), undergo blood sampling

and a chest radiograph. Participants can withdraw at any time without giving a reason. Participants will also be consented for recall by selected genotype or phenotype to obtain additional peripheral blood samples within the five-year lifetime of this study for in vitro mechanistic studies (see secondary objectives).

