9.1. Sample size and statistical power

We will recruit 400 LTBI contacts of active pulmonary TB cases to address the primary objective. This sample size is derived from estimated progression from LTBI to active TB within 2 years of 5%, giving 20 progressors and 380 non-progressors. Progressive disease may be due to a range of different immune responses, and each variation may only be evident in a subset of cases. Therefore, conventional differential gene expression analysis in the TST between groups of progressors and non-progressors, may not identify statistically significant differences. Instead, we will undertake supervised outlier profile analysis to identify gene expression among subsets of progressors, which lies outside the normal range measured in non-progressors. These methods provide robust statistical confidence by incorporating multiple testing corrections³²⁻³⁶, and have been successfully applied to discovery of novel oncogenic pathways^{32,37}. Using preliminary TST transcriptomic data from HIV negative individuals in computational simulations, we estimate >0.8 statistical power in this sample size to detect significant outlier traits among progressors (false discovery rate <0.05) when the outlier trait is shared by 5 or more progressors (Figure 2A). In order to identify eQTLs of TST transcriptomic data, we estimate that a sample size of 1000 is required to give >90% power to detect statistically significant correlations ($p < 10^{-8}$) for allelic frequencies $\geq 5\%$ depending on the correlation coefficients, as a composite measure of effect size and variance⁶¹. Finally, from our pilot data, we estimate that 15% of these individuals will express the blood transcriptional biomarker at time of recruitment to the study. Of these estimated 150 participants, 80 will be recruited to the LTBI treatment sub-study. Conservatively assuming that only 25% of patients decline LTBI therapy, a sample size of 68 participants will provide 80% power to detect a difference of 0.8 standard deviations (SDs) in signature scores between those who accept and decline treatment at each time point. This calculation assumes similar standard deviations among individuals in both groups. We have estimated 0.8SDs as the minimum difference in signature scores that is likely to be of clinical significance (based on the difference in mean scores between IGRA-positive and IGRA-negative TB case-contacts in our pilot data. To allow for losses to follow-up, 80 participants will be recruited.

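### The weight-loss item does not separate intended from unintended loss, yet a yes on it can supply part of the progressor label used in the primary analysis

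*Protocol*

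**What the plan says.** Appendix 5 of the Protocol has three yes/no items. The cough item carries a minimum duration and the night-sweat item a descriptor of severity. The weight item is only "Have you lost weight in the last 3 months", with no amount and no reference to intent.

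Appendix 6 uses the answers in two end points. One is "Two yes answers in the symptom questionnaire", with nothing further required. The other is a change on the chest radiograph "consistent with progressive/active TB with at least one yes answer in the symptom questionnaire". Either one ends participation and leads to routine clinical assessment.

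Section 5 connects these end points to the analysis: participants who develop a positive blood biomarker or "reach a study end point (Appendix 6) as a surrogate for progressive TB before 2 years, will be identified as progressors". It gives no step by which the later clinical assessment can remove the label.

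Follow-up runs at "three monthly intervals for two years", and the questionnaire is completed at each visit.

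The case record form (Appendix 11) has no weight field at any study visit; in the Protocol, weight as a value is asked for only on the serious adverse event form. Most rows print "Weight loss in the last 3 months". The 9-month row of the longitudinal study and the 12-week row of the treatment sub-study print "Weight in the last 3 months".

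**The concern.** In a screening question, loose wording is harmless if a later step filters the answers. Here the answer is part of the case definition for the primary objective. Weight loss by intention is a common and benign reason for a yes, and the plan collects nothing that would let an analyst recognise it afterwards.

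The case group is small. Section 9.1 plans 20 progressors, and its power statement is for an outlier trait shared by 5 or more of them. A handful of people without progressive TB would be a visible share of such a group. They would also leave follow-up early, so their later course would not be observed under the study schedule. The linkage to national surveillance records in section 9.2 is described for the cross-sectional group, withdrawals and losses to follow-up, not for people who leave through an Appendix 6 end point.

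**Working it through.** **The plan's own figure.** Section 9.1 says "We will recruit 400 LTBI contacts of active pulmonary TB cases to address the primary objective" and assumes 5% progression in 2 years. 400 × 0.05 = 20 progressors and 400 − 20 = 380 non-progressors, which agrees with the plan.

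**Inputs from the Protocol.** 380 non-progressors. Eight follow-up questionnaires (months 3 to 24), of which 7 fall before 24 months. The 7 are used because section 5 requires the end point before 2 years.

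**Inputs that are assumptions.** The Protocol gives no rate of yes answers in people without TB. All per-visit rates below are assumed, and answers are taken as independent between items and between visits. Radiographic changes are left out.

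**Calculation A: end points that need the weight item.** Let w be the per-visit chance of a non-TB yes on weight, and s the chance of a yes on cough or sweats. Expected false progressors = 380 × (1 − (1 − w·s)^7).

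| w | s | False progressors | Share of labelled progressors |
|---|---|---|---|
| 1% | 1% | 0.3 | 0.3/20.3 = 1% |
| 10% | 2% | 5.3 | 5.3/25.3 = 21% |
| 20% | 5% | 25.8 | 25.8/45.8 = 56% |

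The share takes all 20 true progressors as labelled. In the middle case, a trait carried by 5 of 20 progressors (25%) becomes one carried by 5 of 25.3 (20%).

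**Calculation B: all symptom end points (any two of three yes).** Let c, n and w be the per-visit rates for cough, night sweats and weight. The per-visit chance is q = cn(1 − w) + cw(1 − n) + nw(1 − c) + cnw, and the expected count is 380 × (1 − (1 − q)^7).

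| c | n | w | q | False end points | Of these, with w = 0 |
|---|---|---|---|---|---|
| 3% | 2% | 10% | 0.00548 | 14.3 | 1.6 |
| 5% | 3% | 20% | 0.01690 | 42.7 | 4.0 |

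The last column is what cough plus sweats would produce without the weight item. The part due to weight is therefore 14.3 − 1.6 = 12.7 to 42.7 − 4.0 = 38.7, or about 13 to 39. If the weight rate were only 2% to 5%, the totals would be 4.2 (3%, 2%, 2%) to 14.0 (5%, 3%, 5%).

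**What was not computed.** The power above 0.8 for the outlier analysis comes from simulations and a figure that are not shown, so the loss of power cannot be derived.

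**The case against.** **Broad wording suits the safety purpose.** The risk table in Appendix 9 describes enhanced 3-monthly follow-up of people whose preventive treatment is deferred. For that use a sensitive question is a reasonable choice. This stands, and it rules out one tempting remedy: requiring a measured loss of a set size inside end points 2 and 3. Reaching the end point is itself what leads to clinical assessment, and the Protocol has no separate rule that refers people on symptoms alone. Such a threshold would change a clinical trigger and could miss true progressors.

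**The case record form rows are typing slips.** This also stands. A reader might infer that two visits do not ask about loss at all. Section 5 has participants complete the Appendix 5 questionnaire, which does ask about loss, and the missing word falls in the third row of both tables. Only the 9-month row can affect the primary label: sub-study entrants are biomarker positive, so those who come from follow-up are already progressors.

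**The size is unknown.** Correct. Yes answers that cluster in the same people would lower the counts.

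**The outlier method is built for subsets.** False cases do not remove the 5 true carriers, so harm to power is plausible but not shown.

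**The root cause is that end point 3 needs no TB confirmation.** If confirmation were added, the wording of this item would matter much less to the label. As the plan is written, no such step exists and the wording does matter.

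**Conclusion.** The point holds as a weakness in the case definition. The weight item cannot distinguish intended from unintended loss, and a yes on it contributes to the progressor label with no stated way to reverse it.

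The number of false progressors cannot be derived from the Protocol. On assumed rates it runs from under 1 to about 43 among 380 non-progressors over 7 visits, with a middle case of about 5 against 20 planned. The upper figure includes about 4 that arise from cough plus sweats alone. The counts cover every non-TB yes on weight, so deliberate loss accounts for an unknown part of them.

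A reader might infer that dieting alone makes a progressor, or that most labelled progressors will be false. The first is wrong, because a second yes or a radiographic change is also needed. The second appears only at the high end of the assumed rates and has no support in the documents.

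**What to change.** 1. Leave the Appendix 6 triggers for ending participation and for clinical assessment unchanged.
2. Add to the case record form, beside the weight item at each visit, whether any reported loss was unintended. Optionally record weight at visits already scheduled.
3. For the primary analysis, do not count intended loss as a yes when assigning the progressor label. Report the label as now written as a sensitivity analysis.
4. Restore the word loss in the 9-month and 12-week rows so that they match Appendix 5.

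The cost is a minor amendment to the form, one extra question per visit and, if chosen, one weighing. It should be made during data collection, because intent and weight at a past visit cannot be reliably recovered later. There is a small downside: a true progressor who attributes the loss to dieting would need another symptom or the biomarker to be counted as a progressor in the primary analysis. The sensitivity analysis shows how much this matters.
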